#### **4.2.2.2 Deaths**

Details of any deaths will be presented in the form of an individual patient listing.

#### **4.2.2.3 Laboratory Data**

For each of the hematological and biochemical test parameters, summary statistics of observed and change from baseline values at each time point will be presented by treatment group for each scheduled time point. For laboratory parameters, post-dose observations on Day 1 will be classed as baseline.

Each observed value will be classified into three categories: Normal (for values within the normal range), High (for values higher than normal) and Low (for values lower than normal). The frequency of each category will be summarized by treatment group for each scheduled time point. Additionally, a shift table will present the changes from baseline at each scheduled time point.

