9.3.2 Estimation Methods for the Primary Estimand/Endpoint

The primary objective for this study is to compare the safety of a single dose of baloxavir marboxil with 5 days of oseltamivir administered BID. All participants exposed to study treatment will be used for safety analyses. Participants will be analyzed according to the treatment they actually received.

Safety will be assessed through summaries of exposure to study treatment, adverse events, changes in laboratory test results, and changes in vital signs.

Study treatment exposure (such as treatment duration, total dose received) will be summarized with descriptive statistics.

All verbatim adverse event terms will be mapped to Medical Dictionary for Regulatory Activities thesaurus terms, and adverse event severity will be graded according to the National Cancer Institute Common Terminology Criteria for Adverse Events (NCI CTCAE) v5.0. All adverse events, serious adverse events, adverse events leading to death, adverse events of special interest, and adverse events leading to study treatment discontinuation that occur on or after the first dose of study treatment (i.e., treatment-emergent adverse events) will be summarized by mapped term, appropriate thesaurus level, and severity grade. For events of varying severity, the highest grade will be used in the summaries. Deaths and cause of death will be summarized.

Relevant laboratory, vital sign (pulse rate, respiratory rate, blood pressure, pulse oximetry, and temperature) will be displayed by time, with grades identified where appropriate. Additionally, a shift table of selected laboratory tests will be used to summarize the baseline and maximum post-baseline severity grade. Changes in vital signs will be summarized.

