### 1.1 TRIAL OBJECTIVES, ENDPOINTS, AND ESTIMANDS

**Table 1 Primary and Secondary Objectives and Corresponding Estimand**

Safety (Primary) Objective	Estimand Definition

To describe the safety of a single dose of baloxavir marboxil compared with 5 days of oseltamivir administered BID in Chinese pediatric participants

	

Population: All participants aged 1 to <12 years with influenza symptoms who received at least 1 dose of study treatment

Endpoint:

Incidence, severity, and timing of adverse events, serious adverse events, with severity determined according to NCI CTCAE v5

Change from baseline in vital sign measurements

Change from baseline in clinical laboratory test results

Treatment:

Experiment arm: baloxavir marboxil single dose

Control arm: oseltamivir 5 days BID

Intercurrent events and handling strategies

Treatment discontinuation: treatment policy strategy

Rescue medication: treatment policy strategy

Population-level summary:

No formal statistical testing will be conducted. Analyses will be descriptive.

Incidence of adverse events, serious adverse events by System Organ Class, by Preferred Term and by worst severity

Change from baseline summaries will be presented overall and by treatment with use of descriptive statistics, including means, standard deviations, medians, and ranges for continuous variables

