### **1.2.1 Treatment Assignment**

This is a randomized, open-label study. After initial written informed consent has been obtained, all screening procedures and assessments have been completed, and eligibility has been established for a participant, the study site will obtain the participant's identification number and treatment assignment from an Interactive Voice/Web-Based Response System (IxRS).

Participants will be randomly assigned in a 2:1 ratio to one of the two treatment arms: a single oral dose of baloxavir marboxil or oseltamivir. Randomization will be stratified by age group (1-<5 years old versus 5-<12 years old) and high risk factors for influenza complications (with versus without), see [Appendix 2](#).

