#### 4.1.1 Visit Windows

**Table 5 Acceptable Time Windows for Parameters Other Than Data from the Patient Diary**

Time Point	Acceptable Time Window
(Scheduled Time Point)	
Pre-dose at Visit 1 (Day 1)	Before dosing on Day 1
Post-dose at Visit 1 (Day 1)	Between 0.5 and 4 hours after dosing (on Day 1)
Visit 2 (Day 2)	Day 2
Optional Visit 1 (Day 3)	Day 3
Visit 3 (Day 4)	Day 4
Visit 4 (Day 6)	Between Day 5 and Day 7 as follows: 

• if patient presents on Day 5 with no Day 4, and no Day 6 this will be classed as Visit 4.

• if patient presents on Day 5 with no Day 4, and Day 6 this will be classed as Visit 3.

• if patient presents on Day 5 with Day 4 and no Day 6 this will be classed as Visit 4.

Visit 5 (Day 10)	Between Day 8 and Day 12
Optional Visit2 (Day 15)	Between Day 13 and Day 22
Visit 6 (Day 29)	On or after Day 23
Withdrawal	Date of withdrawal + 14 days

\* if time is missing for data collected on Visit 1 where, per the schedule of activities, this data should be collected at 'v1 screening' or 'v1 post-dose' it is defined as 'Pre-dose at Visit 1 (Day 1)' or 'Post-dose at Visit 1 (Day 1)' respectively.

Measurements collected within the acceptable time window for each scheduled assessment time point, including data obtained at the time of withdrawal, will be used for the analyses of all endpoints at each assessment time point. For all patients with multiple values within a visit window, the value obtained closest to the target time point will be used. If two measurements collected with the same time deviation exist before and after the target time point, the measurement obtained before the target time point will be adopted for analysis. The assessment time point having no measurements within the corresponding acceptable time window will be considered as missing.

For summaries of data not collected by visit, such as adverse events, medical history and concomitant medications, all data up to the study completion/discontinuation date will be included.

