## 4.2 PRIMARY ENDPOINT(S)/ESTIMAND(S) ANALYSIS

### 4.2.1 Definition of Primary Estimand/Endpoints

The primary endpoint/estimand is to compare the safety of a single dose of baloxavir marboxil with 5 days of oseltamivir administered twice a day (BID), as defined in [Table 1](#).

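### SAP 4.2.2.3 drops the protocol's graded, worst-value laboratory shift without declaring it, and neither document plans a summary of adverse-event timing

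*SAP*

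**What the plan says.** **Laboratory data, protocol.** Protocol 9.3.2 says that relevant laboratory and vital-sign results "will be displayed by time, with grades identified where appropriate", and that "a shift table of selected laboratory tests will be used to summarize the baseline and maximum post-baseline severity grade".

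**Laboratory data, SAP.** Section 4.2.2.3 gives summary statistics of observed values and changes by arm and visit. It then sorts values against the reference range: "Each observed value will be classified into three categories: Normal (for values within the normal range), High (for values higher than normal) and Low". The shift table is also by visit. No grade and no worst post-baseline value is mentioned. Where one visit window holds several values, SAP 4.1.1 (Table 5) states that "the value obtained closest to the target time point will be used".

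**Status of the SAP.** Section 1 gives the SAP precedence over the protocol for the regulatory filing and declares that the planned analyses are unchanged.

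**Adverse-event timing.** SAP Table 1, like Protocol Table 3, defines the first primary endpoint as "Incidence, severity, and timing of adverse events, serious adverse events", graded by CTCAE v5.

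**Aim.** SAP 4.2.1 reads "The primary endpoint/estimand is to compare the safety of a single dose of baloxavir marboxil", and Protocol 9.3.2 also uses *compare*. The objective in Protocol Table 3 and SAP Table 1 is to *describe* safety relative to oseltamivir, without testing.

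**The concern.** Laboratory change is one of three listed components of the primary safety endpoint, beside adverse events and vital signs. For drug safety, the usual question is how many children in each arm reached each grade at their worst. The protocol plans that table. The SAP, which governs the filing, does not, and its statement of no changes means that a reader would not know the table had gone.

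Timing matters because the arms differ in exposure. Baloxavir is a single dose on Day 1. Oseltamivir runs to the evening of Day 5, or to the morning of Day 6 when the first dose is taken after 16:00. Incidence totals to Day 29 cannot show whether events cluster during or after dosing.

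**Working it through.** **1. The plan's own figure.** The only calculated safety figure is the chance of seeing at least one event among 67 baloxavir participants, 1 − (1 − p)^67. At p = 3% this is 1 − 0.97^67 = 87.0%, against 87% stated. For 1% to 5% it gives 49.0, 74.2, 87.0, 93.5 and 96.8%, against 49, 74, 87, 94 and 97%. All agree. This figure does not bear on the laboratory table.

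**2. The two laboratory plans side by side.**

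| Feature | Protocol 9.3.2 | SAP 4.2.2.3 with 4.1.1 |
|---|---|---|
| Scale | Severity grade | Low, Normal or High |
| Post-baseline value | Highest grade reached | Value at each visit; nearest to target if several |
| Tests | Selected | All haematology and biochemistry |

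The SAP covers more tests, but with a coarser scale and no worst value.

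**3. What the scale loses.** An ALT just above the upper limit and one more than three times that limit (the transaminase threshold in Protocol A3–7.6) both fall in High. Counts per grade cannot be recovered from these categories.

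**4. What the visit rule loses.**
- Protocol Table 1 has mandatory laboratory tests only on Day 1 post-dose, which the SAP uses as baseline, and on Day 6. Days 15 and 29 are conditional.
- Protocol 8.2.3 requires clinically significant abnormal values to be repeated until they resolve or stabilise.
- The Visit 4 window covers Days 5 to 7. If a child has a Day 6 value and a worse repeat on Day 7, the rule keeps Day 6.
- A repeat on Days 8 to 12 maps to Visit 5, where no laboratory test is scheduled. The SAP does not say whether it would be tabulated.
- For a child without repeats or conditional tests, the Day 6 value is the only post-baseline value, so worst and scheduled coincide. The main loss is therefore the grade.

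**5. Whether other tables fill the gap.** They do so in part. An abnormality associated with influenza is not an adverse event unless judged more severe than expected (Protocol A3–7.4). The liver event of special interest needs raised ALT or AST together with raised bilirubin or jaundice, so an isolated ALT rise need not appear there.

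**6. Timing.** SAP 4.2.2.1 lists summaries by system organ class, preferred term, severity, relatedness, outcome, action taken and special interest. None covers onset, time to onset or duration. Protocol 9.3.2 and the population-level summaries in both estimand tables have none either.

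**7. Precision, if a difference were reported.** The 95% half-width for a risk difference is 1.96 × √[p(1 − p)(1/67 + 1/33)], with a common incidence p. The documents give no rates, so p is assumed:
- p = 3%: 7.1 points
- p = 10%: 12.5 points
- p = 20%: 16.7 points
- p = 50%: 20.8 points

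A Newcombe interval for 7/67 against 3/33 gives a similar picture: +1.4 points (−14.1 to +12.6).

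**The case against.** The strongest reply is that little is lost. SAP 4.2.2.3 still reports summary statistics, and SAP Table 1 includes ranges, so an extreme scheduled value would be visible. Clinically significant abnormalities not attributed to influenza are recorded as adverse events, graded by CTCAE and tabulated by severity. Cases meeting Hy's Law have their own summary. With one mandatory post-baseline laboratory day, worst and scheduled values coincide for most children, and the protocol limited its shift to selected tests. All of this stands and makes the loss partial. It does not replace a count of children by grade, and it does not make the statement of no changes correct.

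Three stronger readings are tempting, and the documents do not support them.

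- *The SAP fails to deliver the primary comparison.* The prespecified summary is descriptive by arm without testing, SAP 4.2.1 refers back to Table 1, and by-arm tables are planned. No between-arm estimate was planned in either document, so none was dropped.
- *All repeat tests and between-visit peaks vanish.* Only competing values in the same window are discarded, and a later repeat may fall in another window. A peak that was never sampled is a limit of the schedule, and no table can recover it.
- *The SAP removed the timing analysis.* The protocol's estimation section never had one, so the gap lies in both documents.

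**Conclusion.** The point holds in limited form. On laboratory data, SAP 4.2.2.3 departs from Protocol 9.3.2 in two ways (no grade, no worst post-baseline value), and SAP Section 1 does not declare it. This affects one of three components of the primary endpoint. Its numerical effect cannot be stated, because the documents give no laboratory abnormality rates. It depends on how many values are High and how many children have repeats.

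On timing, a named part of the primary endpoint has no planned summary in either document. *Compare* against *describe* is an inconsistency of wording.

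Risk differences with 95% intervals would be a useful option, since 67 against 33 children leaves wide uncertainty (half-width about 12.5 points at an assumed 10% incidence and 20.8 at 50%). They are not a correction. Stratified estimates, intervals on Kaplan-Meier medians and a high-risk subgroup are likewise optional. Age group is already a safety subgroup in SAP 4.5.4.

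One assumption: the protocol's laboratory sentence does not name its grading scale. I read it as CTCAE v5.0, the scale that both documents name for severity.

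**What to change.** 1. In SAP 4.2.2.3, restore a shift table from baseline to worst post-baseline CTCAE grade by arm. List the selected tests and use every post-baseline value, including unscheduled repeats, so that the closest-to-target rule does not apply to this table. Keep the Low/Normal/High tables as they are. If the sponsor prefers not to restore it, declare and justify the removal. Section 1 must then no longer say that nothing has changed.
2. In SAP 4.2.2.1, add a summary of adverse-event onset by arm, for example Days 1–5, 6–10 and 11–29. The cut points are a choice, and some children take their last oseltamivir dose on Day 6.
3. Use one wording for the aim in Protocol 9.3.2, SAP 4.2.1 and the estimand tables.
4. Optionally, report risk differences with 95% intervals for main adverse-event categories, labelled as estimation and not testing.

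The cost is a few extra tables, with no testing and no change in sample size. No new data are needed: local laboratory ranges are collected (Protocol A1–5), clinically significant results from extra local tests must be entered on the eCRF (Protocol 8.2.3), and the SAP already uses adverse-event onset dates.

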#### **4.2.2.4 Vital Signs**

Vital signs (pulse rate, respiratory rate, blood pressure) and change from baseline will be summarized by each scheduled time point. Baseline is defined as the last assessment prior to treatment.

#### **4.2.2.5 Body Temperature**

Body temperature is collected in the patient diary 4 times daily for Day 1 -3, twice daily for Day 4 - 9 and once daily thereafter. Summary statistics of observation and the change from baseline in body temperature will be presented by treatment group for each recorded time point. Baseline is defined as the first recorded assessment after treatment on Day 1.

### **4.3 SECONDARY ENDPOINTS/ESTIMANDS ANALYSES**

#### **4.3.1 Efficacy Secondary Endpoints/Estimands**

The efficacy endpoints/estimands are specified in [Table 1](#).

The CARIFS questionnaire data and body temperature are recorded by participant diary. This assessment data will be recorded for the following time periods:

Period	Time
Morning	05:00 – 10:59
Noon	11:00 – 14:59
Evening	15:00 – 18:59
Bedtime	19:00 – 23:59

In the case where the recorded time of an assessment is outside the period time window for that assessment, the actual assessment time will be used in the analysis.

Details of the analysis methods for these endpoints are listed below.

#### **4.3.1.1 Time to Alleviation of Influenza Signs and Symptoms**

Time to alleviation of influenza signs and symptoms (TTAS) in hours, will be summarized using descriptive statistics by treatment, as well as Kaplan-Meier plots.

It is defined as the length of time taken from the start of treatment to the point at which all of the following criteria are met and remain so for at least 21.5 hours:

- A score of 0 (no problem) or 1 (minor problem) for cough and nasal symptoms (items 14 and 15 of the CARIFS questionnaire, see [Appendix 1](#)).
- A “yes” response to the following question on the CARIFS: “Since the last assessment has the subject been able to return to day care/school, or resume his or her normal daily activity in the same way as performed prior to developing the flu?”
- Return to afebrile state (tympenic temperature  $\leq 37.2$  °C).

If a score of 4 (“don’t know” or “not applicable”) occurs at any assessment for items 14 or 15, the assessment will not be included in the calculation of the alleviation of symptoms.

Patients who do not experience endpoint prior to completion or withdrawal from study will be censored at the last observation timepoint.

Baseline is defined as the first CARIFS assessment after start of treatment on Day 1.

Patients with symptom scores  $\leq 1$  for both items 14 and 15, as well as tympanic temperature  $\leq 37.2$ °C and a “yes” response to the question “Since the last assessment has the subject been able to return to day care/school, or resume his or her normal daily activity in the same way as performed prior to developing the flu?” at baseline will be excluded from the analysis.

The number of patients with completed CARIFS as well as the number with missing CARIFS per assessment, will be presented by treatment. Additionally, the number and percentage of those with “don’t know/not applicable” per question per assessment will be presented by treatment.

#### **Supplementary Analyses**

In the main analysis of the TTAS, only complete assessments (i.e., assessments that have responses for items 14 and 15 of the CARIFS questionnaire, the normal daily activity question and temperature) that do not have scores of 4 for items 14 and 15 are considered in the calculation of the TTAS. A supplementary analysis will be conducted that considers all assessments in the calculation of the TTAS, where a score of 4 for items 14 or 15 does not break the incidence of alleviation.

Another supplementary analysis will be conducted in which the following criterion will be removed from the calculation of the TTAS:

- A “yes” response to the following question on the CARIFS: “Since the last assessment has the subject been able to return to day care/school, or resume his or her normal daily activity in the same way as performed prior to developing the flu?”

In addition, analyses based on virus type and subtype may be conducted if there are a sufficient number of patients with each type/subtype.

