- ^j The parent/caregiver will complete the CARIFS questionnaire twice a day (morning and evening) on Days 1–9 and then once a day on Days 10–15. The results will be recorded in the participant diary.
- ^k A complete physical examination will be conducted at screening. Limited, symptom-directed physical examinations will be performed postdose. Height and body weight will be measured at screening only.
- ^l Conduct assessment if the investigator determines that influenza symptoms or viral shedding are persisting or at the investigator's discretion.
- ^m Vital signs will be recorded if abnormal physical examination findings or adverse events are recorded since the last visit or at the investigator's discretion on Day 29.
- ⁿ *Respiratory samples will be collected using nasopharyngeal or nasal swabs. At each swab timepoint, a virology test will be performed by the central laboratory.*
- ^o PK samples will be collected in baloxavir marboxil treated participants and sent to a central laboratory.

Table 1 Schedule of Activities (cont.)

-
- ^p PK samples will be collected at Day 1 (1 sample between 0.5 and 2 hours postdose). Participants will be assigned to have either the Day 2 (24 hours postdose) or the Day 4 sample (72 hours postdose). Only 1 sample from Days 6–10 is required and can be collected at either Visit 4 or Visit 5.
- ^q After informed consent has been obtained but prior to initiation of study treatment, only serious adverse events caused by a protocol-mandated intervention should be reported. After initiation of study treatment, all adverse events will be reported until 28 days after the first dose of study treatment. After this period, the Sponsor should be notified if the investigator becomes aware of any serious adverse event that is believed to be related to prior exposure to study drug (see [Appendix 3](#)).

Table 2 Schedule of Pharmacokinetic Samples

| Visit Day | Timepoint | Sample Type |
|--------------------|---|--------------------|
| Day 1 | One sample between 0.5 and 2 hours postdose | Drug PK (plasma) |
| Day 2 ^a | 24 hours postdose | Drug PK (plasma) |
| Day 4 ^a | 72 hours postdose | Drug PK (plasma) |
| Days 6–10 | Only 1 sample is to be collected at visit Day 6 or Day 10 | Drug PK (plasma) |

PK=pharmacokinetic.

^a Participants will be assigned to have either the Day 2 or Day 4 sample taken.

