## 1.2 STUDY DESIGN

This is a multicenter, randomized, open-label, active-controlled (i.e., oseltamivir) study to assess the safety, pharmacokinetics, and efficacy of baloxavir marboxil compared with oseltamivir in Chinese pediatric participants aged 1 to  $<12$  years with influenza symptoms within 48 hours of symptom onset.

Approximately 100 pediatric participants are planned to be enrolled. Of the overall sample size, approximately 1/3 participants who are 1 to  $<5$  years old and 2/3 participants who are 5 to  $<12$  years old are planned to be enrolled.

Participants will be screened and randomized on Day 1 and assigned in a 2:1 ratio to receive a single oral dose of baloxavir marboxil based on body weight (2 mg/kg for participants weighing  $<20$  kg or 40 mg for participants weighing  $\geq 20$  kg to  $<80$  kg or 80 mg for those weighing  $\geq 80$  kg) for oral suspension or oseltamivir (twice a day dose based on body weight) for 5 days. Re-screening of participants who fail to meet the inclusion and exclusion criteria will not be permitted for the same illness.

episode, as the time from symptom onset to the treatment window is limited to 48 hours. Either drug will be started at the time of randomization.

The total study duration for each participant will be 29 days, consisting of a 5-day treatment period (mandatory visits on Days 1, 2, and 4) and a 24-day follow-up period (mandatory visits on Days 6, 10, and 29). For the following assessments at clinic visits: physical examinations, vital signs, adverse events, concomitant therapies, clinical laboratory tests, and nasal/throat swabs. Visits on Day 29 or early termination visits can be conducted remotely. Throughout the treatment follow-up periods, the parents/caregivers will maintain a participant diary for each participant in order to record body temperatures (tympanic assessment), influenza symptoms, and acetaminophen use.

Temperatures will be recorded as follows:

- Days 1–3: 4 times daily (morning, noon, evening, and bedtime);
- Days 4–9: twice a day (morning and evening);
- Days 10–15: once daily.

Influenza symptoms will be recorded as follows:

- Days 1–9: twice a day (morning and evening)
- Days 10–15: once a day.

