#### **4.3.1.2 Duration of Fever**

Duration of fever will be summarized using descriptive statistics by treatment, as well as Kaplan-Meier plots. It is defined as the time from the start of treatment to return to afebrile state (tympanic temperature  $\leq 37.2$  °C) and remaining so for at least 21.5 hours. Patients who did not return to afebrile state will be censored at the last observation timepoint. Patients who are afebrile at baseline (tympanic temperature  $\leq 37.2$  °C) or whose body temperature is not collected will be excluded from the analysis.

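### Read literally, the complete-assessment rule leaves noon and bedtime temperatures on Days 1–3 out of the main TTAS analysis, so a fever at those times cannot break the 21.5-hour run

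*SAP*

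**What the plan says.** SAP 4.3.1.1 measures TTAS from the start of treatment to the point at which "all of the following criteria are met and remain so for at least 21.5 hours". The criteria are cough and nasal scores of 0 or 1, a yes to the question on normal daily activity, and a tympanic temperature of 37.2 °C or below.

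Under Supplementary Analyses in the same section, the SAP describes the main analysis: "only complete assessments (i.e., assessments that have responses for items 14 and 15 of the CARIFS questionnaire, the normal daily activity question and temperature" and without a score of 4 on items 14 and 15 "are considered in the calculation of the TTAS". It then plans a supplementary analysis of all assessments, and explains only that a score of 4 on those items does not interrupt alleviation.

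The two diary schedules differ in the first three days. SAP 1.2 sets temperature at "Days 1–3: 4 times daily (morning, noon, evening, and bedtime" and CARIFS at "Days 1–9: twice a day (morning and evening". SAP 4.2.2.5 repeats the temperature schedule, and footnote j of Table 1 in Protocol 1.3 repeats the CARIFS schedule.

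Duration of fever (SAP 4.3.1.2) is "the time from the start of treatment to return to afebrile state", sustained for 21.5 hours. It carries no complete-assessment rule.

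**The concern.** No CARIFS is scheduled at noon or bedtime, so a record from those times has a temperature but lacks items 14 and 15 and the activity answer. If the main TTAS analysis looks only at complete assessments, that temperature is not used, and a fever recorded then cannot interrupt a run of alleviation. The SAP has no rule that pairs such a reading with a CARIFS or lets it break a run by itself.

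Two things are at stake. The derived TTAS may not match its own definition, because a child can be recorded as afebrile for 21.5 hours while the diary shows fever inside that period. Two related endpoints may also disagree: TTAS requires the fever to have ended, yet it could come out shorter than duration of fever in the same child. TTAS is the first efficacy endpoint listed in SAP Table 1 and is also analysed by subgroup (SAP 4.5.4).

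The pattern is foreseeable. Acetaminophen is permitted on Days 1–29 (Protocol 6.1.3) and its use is handled by treatment policy, so readings that dip and rise again are to be expected.

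**Working it through.** The plan states no figure that depends on this rule, so there is none to reproduce. The check lays the two schedules on one grid.

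**Readings left out.**
- Days 1–3: 4 × 3 = 12 scheduled temperatures, of which noon and bedtime make 2 × 3 = 6.
- Days 1–15: 12 + 6 × 2 + 6 × 1 = 30 scheduled temperatures, so 6/30 = 20%. From Day 4 the temperature and CARIFS schedules coincide.
- On Day 1 only postdose diary windows are completed (Protocol Table 1, footnote i). A dose between the morning and noon readings leaves 6 of 11. A dose between noon and evening leaves 5 of 10.

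**Can a run be confirmed without a noon or bedtime slot inside it?** The windows in SAP 4.3.1 are morning 05:00–10:59, noon 11:00–14:59, evening 15:00–18:59 and bedtime 19:00–23:59. Within them, evening to the next morning is at most 15:00 to 10:59, or 19 h 59 min, and morning to the same evening at most 05:00 to 18:59, or 13 h 59 min. Both are below 21.5 h. A run therefore needs at least three successive morning or evening records. It always spans a bedtime slot and a noon slot, as far as those are scheduled.

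**Readings per run.** Assume clock times of 08:00, 13:00, 17:00 and 21:00. The shortest qualifying run is then 24 h. One starting between Day 1 evening and Day 3 morning holds 5 temperatures, 2 of them unused. One starting on Day 3 evening holds 4, with 1 unused. Runs starting later are unaffected.

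**Effect in one child.** Assume in addition a dose at 10:00 on Day 1, fever throughout Day 1, no fever after Day 2, and the cough, nasal and activity criteria met throughout. A run starts at a morning or evening record, and TTAS is the time from dose to that start.
- Day 2 morning: 24 + 8 − 10 = 22 h
- Day 2 evening: 24 + 17 − 10 = 31 h
- Day 3 morning: 48 + 8 − 10 = 46 h

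| Readings above 37.2 °C on Day 2 | TTAS, complete assessments only | TTAS, any temperature can break the run | Difference |
|---|---|---|---|
| Noon and bedtime | 22 h | 46 h | 24 h |
| Bedtime only | 22 h | 46 h | 24 h |
| Noon only | 22 h | 31 h | 9 h |

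Duration of fever, taken from all temperatures, is 46, 46 and 31 h in these children. Under the literal rule TTAS is shorter than duration of fever in each case. The direction is fixed, because the unused readings can only break a run, never create one.

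**How many children could be exposed.** On the same clock times the last affected run starts on Day 3 evening, at 48 + 17 − 10 = 55 h. Protocol 2.3 gives a median of 138.1 h for the symptom endpoint in the baloxavir arm of the earlier pediatric trial. If that median applied here, with an assumed Weibull shape k, the share alleviated by 55 h would be 1 − exp(−ln 2 × (55/138.1)^k):
- k = 1 (exponential): 24%
- k = 1.5: 16%
- k = 2: 10%

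This caps who could be affected under those assumptions. It does not estimate how many are, because only children with an intervening noon or bedtime fever count, and the documents do not give that number.

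**The case against.** The strongest reply is that the SAP never says these readings are discarded. The term assessment is not defined. The completeness sentence introduces an analysis concerned with score-4 answers, so it may have been meant for CARIFS records only, and on a plain reading of the definition a bedtime fever breaks the run. This stands to the extent that the point rests on a literal reading. Against it, the sentence names temperature as part of a complete assessment, whereas the parallel rule for duration of symptoms (SAP 4.3.1.3, Supplementary Analyses) lists only CARIFS symptoms. Two programmers could reasonably derive different values.

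A second reply is that the supplementary analysis of all assessments brings the readings back. It might, if a temperature-only record counts as an assessment. But the SAP spells out only the score-4 handling, and the main analysis would be unchanged.

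Third, few children may qualify. They must be afebrile at every morning and evening reading in the run and also meet the cough and nasal criteria. The activity question asks about the interval since the last assessment, so a yes must cover the febrile hours. This stands and limits the size.

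Fourth, using only paired readings gives the same ascertainment on every day from Day 1 to Day 9. That is a defensible choice if stated, but it is not stated, and it does not fit a definition that requires the afebrile state to persist.

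A reader might also infer that the comparison between arms is biased. The documents do not support that: the rule is the same in both arms, and nothing shows that intermittent fever differs between them.

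**Conclusion.** The point holds as a gap between the stated rule and the endpoint's definition. Read literally, the rule leaves up to 6 of 12 scheduled temperatures on Days 1–3 out of the main TTAS analysis. A child with fever only at those times could be counted as alleviated too early, by 9 to 24 h in the worked examples, and could have a TTAS shorter than the duration of fever.

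The error can only shorten TTAS and is confined to runs starting by about Day 3 evening. The number of children affected is unknown and the shift in the median may be small. The hour figures rest on assumed clock times and a 10:00 dose. The 10–24% rests on an assumed distribution and on the earlier trial's median, and should not be taken as a misclassification rate.

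Nor should TTAS be read as the trial's main endpoint. It is secondary, the primary objective is safety, the analyses are descriptive and no hypothesis is tested, so no error rate is affected. Within those limits the text should be corrected before database lock.

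**What to change.** In SAP 4.3.1.1, state three things:
- The complete-assessment rule applies to CARIFS items 14 and 15 and the activity question.
- The afebrile criterion uses every temperature recorded in the diary, including noon and bedtime on Days 1–3.
- Any temperature above 37.2 °C within the 21.5-hour period breaks alleviation, whether or not a CARIFS was completed at that time.

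The version based on paired morning and evening readings can be kept as a sensitivity analysis.

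The cost is a short addition to the SAP and a small programming change, with no new data collection. TTAS becomes slightly longer in some children. Days 1–3 will offer more readings that can break a run than Days 4–9 (four a day against two), which the report should mention.
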